3.2.2 Secondary Outcome Measures

- Adverse event occurrence
- Facial Image Scale score (1-5)

4. Study Design

This is a single center randomized, double-blind, placebo-controlled, parallel-group trial.

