4.1 Rationale for Study Design

The hypothesis is that the test varnish will be superior to the control varnish and will not be inferior in patient response than the control varnish. There will be no difference in the frequency of adverse events.

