8.3 Safety Assessments

Adverse events, including frequency and severity, and perceived relationship to the investigational product, will be compared between the treatment groups.

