11.1 Study Hypotheses

The hypothesis is that the test varnish will be superior to the control varnish and will not be inferior in patient response to the control varnish. Also, there will be no difference in the frequency of adverse events.

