11.3 Statistical Analysis Plan

11.3.1 Primary Statistical Analysis.

The primary analysis will be conducted in accordance with the intention-to-treat principle, and multiple imputation procedures will be used to account for missing caries information (Schafer, 1997). For the primary outcome, incremental dental caries based on d₂₋₃mfs/DMFS, the unit of analysis will be the child and the mean dental caries increment will be compared between the two interventions separately at 1 and 2 years post baseline using a two-sample t test assuming unequal variances. This approach assumes the distribution of dental caries increment is approximately symmetrical, which is often true in high-risk caries populations. In this case, non-symmetry, log-linear regression using robust standard errors, which can accommodate count outcomes with skewed distribution, will be used to compare the caries rates between the two interventions (Hardin & Hilbe, 2003). Covariate-adjusted linear (or log-linear) regression models using robust standard errors will be used to compare dental caries increment, adjusting for baseline dental caries, stratification variables (education center and school), gender and age of the participant (Hardin and Hilbe, 2003). Analyses will be performed using R (The R Foundation for Statistical Computing, 2016; Version 3.3.0) and SAS (SAS Institute, Cary, NC, Version 9.4).

11.3.2 Analysis of Safety Data.

Adverse events (AEs) will be tabulated by treatment group, severity, and perceived relationship to investigational product. For each AE, treatment group comparisons regarding the occurrence of at least one event will be made using Fisher's exact tests. The comparisons will be repeated excluding all mild symptoms. Similar analyses will be performed after grouping AEs by body system using standard Medical Dictionary for Regulatory Activities (MedDRA) coding. Individual AEs will be listed, with particular attention paid to serious AEs.

11.3.3 Participant Disposition.

The frequency and reasons for withdrawal will be summarized by treatment group, as will the number of missed visits and missed treatment applications (compliance).

12. Source Documents and Access to Source Data/Documents

The site will maintain appropriate medical and research records for this trial, in compliance with ICH E6, Section 4.9 and regulatory and institutional requirements for the protection of confidentiality of subjects.

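### Adverse event frequency is to be compared between arms but is not defined, and the only planned test (at least one event) cannot see repeat events over eight applications

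*Combined protocol and SAP*

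**What the plan says.** The safety hypothesis appears twice. Section 4.1 states: "There will be no difference in the frequency of adverse events". Section 11.1 repeats it: "Also, there will be no difference in the frequency of adverse events". Section 8.3 turns it into a planned comparison: "Adverse events, including frequency and severity, and perceived relationship to the investigational product, will be compared between the treatment groups". None of these sections says whether frequency means a number of events, a rate, or a proportion of children.

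The outcome list in 3.2.2, like the Protocol Summary, names the safety outcome as "Adverse event occurrence".

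The analysis is in 11.3.2. It begins with a description: "Adverse events (AEs) will be tabulated by treatment group, severity, and perceived relationship to investigational product". The unit of these tables, children or events, is not given. The only formal comparison is then set out: for each type of event, "treatment group comparisons regarding the occurrence of at least one event will be made using Fisher's exact tests". This is extended in two ways. One is a repeat without mild events ("The comparisons will be repeated excluding all mild symptoms"), and the other is a similar analysis by MedDRA body system. Individual events are also listed. No comparison of counts or rates is planned.

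Sections 7.2 and 7.3 have varnish applied at the first treatment visit and at visits 2 to 8.

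**The concern.** The hypothesis is one of no difference in frequency, so a non-significant result from an insensitive test is likely to be read as support for it. An at-least-one-event test is insensitive in two situations that repeated dosing makes possible. In the first, the arms have similar numbers of affected children but differ in how often those children are affected. In the second, an event is common enough that most children in both arms have had it once by the eighth application. The second matters for the body-system groupings and for any overall total, because section 9.3 counts unrelated illnesses and accidents over the study as adverse events.

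The tables and listings may show repeats. Nothing in 11.3.2, however, yields a between-arm estimate of event frequency with a confidence interval that allows for several events in one child.

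**Working it through.** **No safety figure to reproduce.** The plan states no alpha, power, event rate or margin for the safety comparison. The sample size in 11.2 concerns caries only and does not bear on this point, except that it supplies a number per arm.

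**Inputs from the documents.**
- Applications per child: first treatment visit plus visits 2 to 8, so 1 + 7 = 8 (sections 7.2, 7.3).
- Children per arm: 280/2 = 140 (section 11.2), or 600/2 = 300 (section 5.1).

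**Assumptions.** Two-sided 0.05, all eight applications received, and every event rate.

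**Tests compared by simulation (2,000 to 3,000 replicates per run).**
- Fisher's exact test on whether a child's count exceeds zero.
- Rate comparison: z = log(m_T/m_C) / sqrt[ s_C²/(n·m_C²) + s_T²/(n·m_T²) ], where m and s² are the mean and variance of events per child. This allows for repeats within a child.

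**Why the binary test weakens.** With independent events at probability p per application, a child has at least one event with probability 1 − (1 − p)^8, and 8p events on average.
- 20% v 25%: ever affected 1 − 0.80^8 = 83.2% v 1 − 0.75^8 = 90.0%; mean events 1.6 v 2.0. The ratio of means is 2.0/1.6 = 1.25, but the ratio of proportions is only 90.0/83.2 = 1.08.
- 2% v 4%: ever affected 1 − 0.98^8 = 14.9% v 1 − 0.96^8 = 27.9%; mean events 0.16 v 0.32. Here the binary outcome keeps most of the contrast.

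**Power at 140 per arm.**

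| Assumed rate per application | Fisher | Rate comparison |
|---|---|---|
| 20% v 25%, independent | 32% | 80% |
| 10% v 15%, independent | 76% | 94% |
| 10% v 15%, within-child correlation 0.1 | 67% | 77% |
| 10% v 15%, correlation 0.2 | 62% | 64% |
| 2% v 4%, independent | 72% | 79% |
| 2% v 4%, correlation 0.1 | 56% | 56% |
| 2% v 4%, correlation 0.2 | 48% | 43% |

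Repeat runs differ by a few percentage points at most. At 300 per arm the first row becomes 64% v 98%. Under no difference, the rate comparison rejected in 4% to 6% of runs.

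**Most favourable case for a rate comparison.** Suppose 20% of children react in each arm, and each reactor reacts again at each later application with probability 5% (control) or 40% (test). Mean events per child are 0.20 × (1 + 7 × 0.05) = 0.27 and 0.20 × (1 + 7 × 0.40) = 0.76. Fisher rejects in 3% of runs and the rate comparison in 97%. If no child contributes more than two events, the 97% falls to about 40%.

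**The case against.** The strongest reply is that outcome and test agree. The outcome is named as occurrence where outcomes are defined, and 11.3.2 tests occurrence. *Frequency* is undefined, and section 11.3.3 uses the same word for withdrawals, which normally happen once per child. A reader might infer that the plan gives one endpoint two conflicting definitions. The documents do not support that reading, and on this the reply stands.

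A reader might also infer that repeat events are lost altogether. They are not: events are recorded at each contact (9.2), tabulated by arm, and listed one by one. Only the formal test ignores repeats. What remains is that the counting unit of the tables is unstated and no estimate of frequency is planned.

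A third tempting inference is that iodine reactions are expected to recur or build up on re-exposure. No section says so. Sections 2.2.1 and 9.4 name rash and swelling at the site and thyroid problems, and 2.2.1 calls the last rare. The point does not need this premise.

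Finally, 3% v 97% should not be read as the size of the problem. That case fixes the proportion of affected children as equal, so Fisher's null hypothesis is true and its 3% is simply its error rate. It also assumes every reactor continues through eight applications, although 5.8 and 9.5.2 allow withdrawal for adverse events. With rare independent events, part of the gap is Fisher's conservatism: in one run at 2% v 4%, Fisher had 72%, an uncorrected chi-square test on the same binary outcome 77%, and the rate comparison 80%. With clustering the advantage disappears or reverses. These objections stand, and they are why the rate comparison should supplement the Fisher test and not replace it.

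**Conclusion.** The point holds in a limited form. The plan states a hypothesis about adverse event frequency, leaves the term undefined, and provides no analysis that estimates events per child or per application. Whichever meaning was intended, the planned test is blind to a difference made up only of repeat events.

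The size depends on event rates that the documents do not give. The loss is large for common, independent events, modest or nil when events are rare, and slightly in Fisher's favour for rare events that cluster strongly in the same children. The phase 1 experience in section 2.1 (12 children, no adverse effects) offers no support for high reaction rates, but it is too small to exclude them. This is a cheap improvement to a secondary safety analysis, not a flaw that invalidates it.

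**What to change.** In 11.3.2:

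1. Keep the Fisher tests as the occurrence analysis.
2. State that every adverse event table shows both the number of children affected and the number of events, and say which of these *frequency* means in 4.1, 8.3 and 11.1.
3. For total adverse events, and for the post-treatment reactions listed in 9.6.1, add the event rate per application by arm. Give the rate ratio and 95% CI from log-linear regression with robust standard errors, with log(applications received) as offset. Label these results descriptive.

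No new data are needed. The Adverse Event Log holds each event with its onset date (9.3), the Drug Accountability Log holds each application (6.3), and the regression method is already named in 11.3.1. The cost is a few sentences, a little programming, and a few more descriptive safety comparisons, which will add little if events prove rare or clustered.

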12.1 Primary Source Documents

The Principal Investigator must maintain primary source documents supporting significant data for each subject in the subject's notes. During monitoring visits, the clinical site monitor will validate data in the CRF against these source data.

12.2 CRF Worksheets

The site will be supplied with a set of forms-based schedule of activities and corresponding source document worksheets (SDW) that correspond to the case report form (CRF) for this study. The worksheets will serve as source documents for study observations. Additional source documentation for information not specifically included on the source document may be recorded on a separate document.

Access to the source documents should be limited to those working on the study. Access to the database will be restricted.

13. Ethics/Protection of Human Subjects

13.1 Ethical Standard

This study will be conducted in accordance with the Good Clinical Practice (GCP) guidelines promulgated by the International Conference on Harmonization (ICH) and the Food and Drug Administration (FDA), and any applicable national and local regulations including FDA regulations under 21 CFR Parts 11, 50, 54, 56, 312 and 314.

The Principal Investigator will ensure that this study is conducted in full conformity with the principles set forth in The Belmont Report: Ethical Principles and Guidelines for the Protection of Human Subjects of Research, as drafted by the US National Commission for the Protection of Human Subjects of Biomedical and Behavioral Research (April 18, 1979) and codified in 45 CFR Part 46 and/or the ICH E6; 62 Federal Regulations 25691 (1997).

13.2 Institutional Review Board

The Western IRB will review and approve the submission activities for the conduct of this protocol. The trial will not begin until the study has been approved by the WIRB, all required regulatory documentation is on file at both the site and the Principal Investigator and staff are trained on the protocol and data capture procedures.

13.3 Amendments

The Principal Investigator will discuss any proposed protocol changes with the Sponsor and no modifications will be made without prior written approval and WIRB approval of the amended protocol, except where clinical judgment requires an immediate change for reasons of subject welfare. The WIRB will be informed of any amendments to the protocol or consent form, and approval (where and when appropriate) will be obtained before implementation.

13.4 Informed Consent Process

This study will be conducted in accordance with the provisions of 21 Code of Federal Regulations (CFR) Part 50.

In accordance with relevant regulations, a parent informed consent agreement explaining the procedures and requirements of the study, together with any potential hazards/risks must be read and/or explained to each parent/guardian. Each subject's parent or legal guardian will sign such an informed consent form. The subject's parent/guardian must be assured of the freedom to withdraw from participation in the study at any time.

It is the Principal Investigator's responsibility to make sure that the subject's parent/guardian understands what he or she is agreeing to and that written informed consent is obtained before the subject is involved in any protocol-defined procedures, including screening procedures. It is also the Principal Investigator's responsibility to retain the original signed consent forms and provide each subject's parent/guardian with a copy of the signed consent form.

As children will be enrolled in this study, the informed consent process will be documented in the form of permission from the parent or legal guardian in the parent permission form; child assent (affirmative agreement by a child to participate in research) will not be employed in this study.

13.5 Exclusion of Women, Minorities, and Children (Special Populations)

This study will enroll children aged 60 to 84 months. There will be no exclusion due to gender, race or ethnicity.

13.6 Subject Confidentiality

The Principal Investigator must assure that the privacy of subjects, including their personal identity and personal medical information, will be maintained at all times. Personal medical information will always be treated as confidential. The parent/guardian's Authorization allows the Sponsor-Investigator to receive and review the subjects' protected health information that may be re-disclosed to any authorized representative of the Sponsor for review of subject medical records in the context of the study.

13.7 Study Discontinuation

At the completion of the study, study closeout procedures will be implemented.

14. Data Handling and Record Keeping

The Principal Investigator is responsible for ensuring the accuracy, completeness, legibility, and timeliness of the data reported.

14.1 Data Management Responsibilities

The Biostatistician will be responsible for all data collection procedures. The Data Management Plan includes, but is not limited to:

- Overview of data management processes utilized for study
- Universal data handling conventions
- Study-specific data handling conventions
- Coding dictionaries and practices
- Specifications for logic and edit checks
- External data handling practices
- Final study closeout activities
- Audit plans
- Sample CRF annotation
- Biostatistician contact information
- Section for tracking revisions to the plan
- Administrative report specifications

The Data Management Plan serves to document the practices and procedures deployed to promote consistent, efficient, and effective data management practices leading to the creation of a high-quality database ready for analysis. The plan serves as the authoritative source, documenting data management practices, and decisions that are agreed to with the Principal Investigator at the start of the study and as necessary updates are made during the conduct of the study.

Data will be transferred periodically from the study site to the University of Washington to prepare reports. At the close of the study, the locked database will be transferred to the Biostatistician for analysis.

The Biostatistician will be responsible for design of the randomization scheme, creation of analytical databases, and the statistical analysis plan.

14.2 Data Capture Methods

Clinical data (including AEs, concomitant medications, and expected adverse reactions data) will be entered into the study database by the Data Manager. This system is protected by 128-bit server certificates and utilizes authenticated, password-protected accounts for each site. The system is compliant with relevant FDA regulatory requirements per 21 CFR Part 11.

14.3 Types of Data

Data for this study will include clinical assessments, safety, and outcome measures (e.g., expected adverse reactions). Safety data are contained in the clinical data set.

14.4 Timing/Reports

Enrollments and **study activity (protocol-specified reportable events)**, as described in Section 9.6.1) reports will be generated as they occur to a pre-determined distribution list that includes the Principal Investigator and team.

Clinical monitoring reports will be generated periodically with electronic distribution to the PI and team. Per the Clinical Monitoring Plan, the clinical monitor reports include routine reports of aggregate, blinded adverse event data for ongoing review by for potential trends, and adverse event and concomitant medication reports for the PI to review for standardization of coding.

Safety monitoring reports will be provided by the Biostatistician per the safety monitoring plan.

Missing data, missing electronic signatures of the Principal Investigator, and requests for **data clarification** reports will be generated to the site on a regular basis.

Monitoring Visit Reports will be generated after each clinical site monitoring visit, per the monitoring plan.

At the completion of the study, data will be securely transferred to the Biostatistician. Once the Biostatistician and the PI agree that all queries have been adequately resolved and the database has been deemed “clean”, the database will be officially signed off and deemed locked. All permissions to make changes (append, delete, modify or update) the database are removed at this time.

All site personnel, Sponsor and staff will remain blinded as to treatment assignments until the conclusion of the entire study. A designated unblinded biostatistician will have access to the treatment assignments, and this individual will not communicate about study-related matters to any other staff involved in the study. The study code will be broken by the study-responsible statistician after all outstanding substantive data queries have been resolved.

14.5 Study Records

14.5.1 Study File and Site Documents

The Principal Investigator should have the following study documents accessible to the Clinical Site Monitor during the study. These records are kept in the study office in Pohnpei.

1. Signed Form FDA 1572
This study will be conducted under the supervision and direction of the Principal Investigator listed in Section 1 of the Form FDA 1572. Sub-Investigators are listed in Section 6 of the Form FDA 1572. The study will be conducted at the address(es) listed in Section 3 of the Form FDA 1572.
2. Curriculum vitae for the Principal Investigator and all personnel listed on Form FDA 1572
The Principal Investigator is responsible for providing copies of the protocol and all other information relating to the preclinical and prior clinical experience, which were furnished to him/her, to all other study personnel who participate in this study. The Principal Investigator will discuss this information with them to assure that they are adequately informed regarding the investigational product and conduct of the study. The Principal Investigator must assure that all study staff members are qualified by education, experience and training to perform their specific responsibilities.
3. The signed IRB form/letter stating IRB approval of protocol, consent forms, and any other study materials (e.g., patient instruction materials, advertisement notices), documentation of the IRB composition, and all IRB correspondence including notification/approval of protocol amendments, notification of serious, unexpected, suspect adverse drug reactions to the IRB, and IRB notification of study termination
4. Training records
Records of protocol-specific training will be maintained.
5. IRB-approved consent form
6. Signed protocol (and amendments, where applicable)
7. Signed parent/guardian permission forms
8. Copies of the completed source document worksheets
9. Delegation Log with names, signatures, initials, and functional role of all persons completing protocol assessments and providing back-up to the Principal Investigator.
10. Accountability of investigational product
11. Record of all monitoring visits by Clinical Site Monitor(s)
12. Copies of correspondence
13. Certificate for Human Subject Protection Program (HSPP) for each individual named on the Delegation Log who has direct subject contact
14. Copy of professional licensure/registration, as applicable, for each individual named on the Delegation Log, who has direct subject contact, ensuring licensure is in the locality in which the study will be conducted
15. The Principal Investigator must also retain adequate documentation, together with the subject's hospital/medical records, as the subject's source data for the study.

14.5.2 Maintenance and Retention of Records

It is the responsibility of the Principal Investigator to maintain a comprehensive and centralized filing system of all relevant documentation. The Principal Investigator will be instructed to retain all study records required by federal regulations in a secure and safe facility with limited access for one of the following time periods based on notification from the Monitor.

The Principal Investigator will be instructed to consult with and provide advance written notice to the Monitor before disposal of any study records and to notify the Monitor of any change in the location, disposition, or custody of the study files. No study document or image should be destroyed without prior written agreement between the Sponsor and the Principal Investigator.

Regulations require retention for:

- A period of at least two years after notification from the Sponsor that a U.S. NDA (New Drug Application) has been approved for the indication that was investigated or 15 years according to International Conference on Harmonization (ICH) guidelines.
- Or, if no NDA is filed or approved for such indication, a period of at least two years after the investigation is completed or discontinued, and the FDA (Food and Drug Administration) has been notified by the Sponsor.

